8.2 Participant demographics/other baseline characteristics

8.2.1 Demographics/medical history

Demographics (including age, sex)/medical history information will be collected at screening and captured in the eCRF.

Any relevant medical history, including relevant hospitalizations from time of birth /current medical conditions (until date of signature of informed consent) will be recorded in the eCRF. Where possible, the diagnosis and not symptoms should be recorded.

All prescription medications, over-the-counter drugs and significant non-drug therapies prior to the start of the study must be documented. See the [Section 6.2.1 Concomitant Therapy](#) for further details on what information must be recorded on the appropriate page of the eCRF.

8.2.2 SMA medical history

Familial history of SMA including affected siblings or parent carriers will be collected. Any relevant SMA medical history, including SMA type and number of *SMN2* gene copies (if available), will be recorded in the eCRF.

8.2.3 Physical examination

Physical examinations will be conducted by the Investigator or designee as specified in the [Table 8-1](#). The Day 1 physical examination will be performed prior to the start of gene replacement therapy infusion. Physical examinations include a review of the following systems: (HEENT), lungs/thorax, cardiovascular, abdomen, musculoskeletal, neurologic, dermatologic, lymphatic, and genitourinary.

Physical examination data will be captured on source documentation.

8.2.4 Neurological examination

Neurological examinations will be conducted by the Investigator or designee as specified in the [Table 8-1](#). Specifically, the neurological exam should include detailed, age-appropriate sensory testing (such as examination of proprioceptive, vibratory, tactile and pain sensation) at each visit. Any clinically significant sensory abnormal finding will be recorded in eCRF.

Further clinical evaluation of sensory abnormalities will include nerve conduction studies per local standard of care including but not limited to sural sensory nerve action potential (SNAP).

8.2.6 Virus serology

The administration of an AAV vector has the risk of causing immune-mediated hepatotoxicity. For participants who have HIV or positive serology for hepatitis B or C, administration of the AAV vector may represent an unreasonable risk; therefore negative serology testing must be confirmed at screening, prior to treatment. These samples will be collected in accordance with the [Table 8-1](#) and shipped in accordance with the laboratory manual provided by the central laboratory.

8.3 Efficacy

The efficacy assessments described below have been selected in order to evaluate the effect of OAV101 on SMA.

8.3.1 Hammersmith Functional Motor Scale-Expanded (HFMSE)

See [Section 8.5.1.1](#) for details.

8.3.2 Revised Upper Limb Module (RULM)

See [Section 8.5.1.2](#) for details.

8.3.3 Developmental milestone checklist

See [Section 8.5.1.3](#) for details.

8.3.4 Video evidence

Video evidence is optional. Parent(s)/legal guardian(s) may provide home videos at any time during the study that demonstrate achievement or maintenance of Developmental Motor Milestone in an effort to confirm compelling, demonstrable, documented evidence of efficacy.

Completion of the Developmental Milestone Checklist for home videos uploaded is required to document achievement of developmental motor milestones between visits. The Developmental Milestone Checklist will contain the date of home video recording.

Novartis will provide a secure process to upload, transfer and store videos through a contracted third-party vendor that will compile as per the sponsor requirements. A secure, encrypted transfer and storage solution will be provided to properly protect the identities of the patient and caregivers on the videos, which may be shared with regulatory agencies, the medical community, and/or in appropriate venues to discuss the results of this clinical trial. Any videos received will be treated as confidential data and will be either the sole property of Novartis or will be permanently licensed to Novartis to use and disclose.

8.3.6 Appropriateness of efficacy assessments

Efficacy assessments for developmental milestones and motor assessments are standard for this indication/participant population.

8.4 Safety

Safety assessments are specified below with the assessment schedule detailing when each assessment is to be performed ([Table 8-1](#)).

Safety parameters include demographics/medical history, physical and neurological examinations, vital signs, height and weight measurements, 12-lead ECGs, echocardiograms, laboratory assessments, and AE monitoring.

For details on AE collection and reporting, refer to [Section 10.1](#).

As per [Section 4.7](#), during a Public Health emergency as declared by Local or Regional authorities i.e. pandemic, epidemic or natural disaster, that limits or prevents on-site study visits, regular phone or virtual calls can occur based on the [Table 8-1](#) assessment schedule for safety monitoring and discussion of the participant's health status until it is safe for the participant to visit the site again.

If participants cannot visit the site for safety lab assessments through central labs, local lab collection may be used and results will be entered in the eCRF.

8.4.1 Laboratory evaluations

A central laboratory will be used for analysis of all specimens collected. Details on the collections, shipment of samples and reporting of results by the central laboratory are provided to Investigators in the laboratory manual.

Safety samples that can be collected remotely will be collected and analyzed in line with the study laboratory manual. Where samples are collected and analyzed at a local laboratory instead of the central laboratory, Novartis will ensure the results reported are equivalent to central laboratory collection and analysis.

If participants cannot visit the site for safety lab assessments conducted through central labs, local lab collection may be used during a Public Health emergency as declared by Local or Regional authorities i.e. pandemic, epidemic or natural disaster, that limits or prevents on-site study visits.

If participants cannot visit the site for protocol specified safety lab assessments, an alternative lab (local) collection site may be used.

8.4.1.1 Hematology

Hematology analysis will include a complete blood count with differential and platelet count. Samples will be collected and shipped in accordance with the laboratory manual provided by the central laboratory. Blood samples for hematology analysis will be collected as specified in the [Table 8-1](#).

Hematology analysis will include the following:

- Hematocrit
- Hemoglobin
- MCH
- MCHC
- MCV
- Platelets
- Red blood cells
- White blood cells
- Differential (Basophils, Eosinophils, Lymphocytes, Monocytes, Neutrophils, Bands)

To monitor platelet counts, hematology analyses required during in-patient dosing, as determined by the Investigator, and on Day 2 prior to discharge, will be performed as per investigational site standard procedures at the local laboratory. Investigators will receive hematology results from all other study visits from the central laboratory. Further, platelet counts should be closely monitored in the week following infusion and on a regular basis afterwards.

In the event that clinically significant and/or moderate or severe thrombocytopenia and anemia are noted, further evaluation to diagnose Thrombotic Microangiopathy (TMA) should be conducted in accordance of standard of care. If a clinical diagnosis of TMA is made, a complete complement panel should be obtained per standard of care.

8.4.1.2 Coagulation panel

Coagulation testing including prothrombin time (PT) and International Normalized Ratio (INR), and activated partial thromboplastin time (aPTT) will be performed prior to OAV101 dosing ([Table 8-1](#)).

8.4.1.3 Blood chemistry

Samples will be collected and shipped in accordance with the laboratory manual provided by the central laboratory. Blood samples for chemistry analysis will be collected as specified in the Schedule of Assessments ([Table 8-1](#)).

Chemistry analysis will include the following:

- Alkaline phosphatase
- ALT
- AST
- GGT
- LDH
- G-LDH
- Bicarbonate
- Calcium
- Phosphorus
- Chloride
- Sodium
- Potassium
- Creatinine
- Creatine kinase
- Direct Bilirubin
- Indirect Bilirubin
- Total Bilirubin
- BUN or Urea
- Glucose

Troponin I will be collected as specified in the Schedule of Assessments ([Table 8-1](#)) as applicable.

Investigators will receive chemistry results from all trial visits from the central laboratory.

If liver aminotransferase elevations occur, the process outlined in [Section 10.2.1](#) should be followed.

8.4.1.4 Urinalysis

Urine samples will be collected in accordance with the laboratory manual provided by the central laboratory at study visits in accord with the Schedule of Assessments ([Table 8-1](#)).

8.4.2 Electrocardiogram (ECG)

8.4.2.1 12-Lead electrocardiogram

A 12-lead ECG will be performed at times indicated in the Schedule of Assessments.

In the case of a series of assessments, ECG should be first assessment obtained while participant is at rest. The preferred sequence of cardiovascular data collection during study visits is ECG collection first, followed by vital signs, and blood sampling.

The Fridericia QT correction formula (QTcF) must be used for clinical decisions.

Unless auto-calculated by the ECG machine, the Investigator must calculate QTcF at the Screening and/or Baseline visit(s) (as applicable) to assess eligibility according to the following formula:

$$QTcF = \frac{QT}{\sqrt[3]{RR}}$$

Triplicate 12-lead ECGs are to be collected with ECG machines available at the site. Each ECG tracing must be labeled with study number, participant initials, participant number, date and time, and filed in the study site source documents. Investigator should document clinical evaluation in source.

The ECG will be interpreted locally by a pediatric cardiologist or designee for immediate safety evaluation. The ECG tracings or ECG machine data will also be collected for centralized review. In the event that a clinically significant ECG abnormality is identified at the site (e.g., severe arrhythmia, conduction abnormality of QTcF > 500 ms), a copy of the assessment is sent to the central ECG laboratory for expedited review and the ECG is repeated to confirm the diagnosis. If the participant is hemodynamically compromised, the investigator or a medically qualified person must initiate appropriate safety procedures without delay.

Additional, unscheduled, safety ECGs may be repeated at the discretion of the investigator at any time during the study as clinically indicated. All ECGs, including unscheduled safety ECGs with clinically relevant findings collected during the study need to be transmitted to the central ECG laboratory for review.

Clinically significant ECG findings at baseline must be discussed with Novartis before administration of study treatment.

Clinically significant abnormalities must be recorded on the relevant section of the medical history/Current medical conditions/AE eCRF as appropriate.

8.4.2.2 Echocardiogram

A standard transthoracic ECHO will be performed at times indicated in the Schedule of Assessments (Table 8-1); these will be interpreted locally by a cardiologist or a designee for immediate safety evaluation. The ECHOs will also be collected for centralized review by a cardiologist. The Novartis physician or designee will be notified of any safety concerns from the centralized review.

8.4.3 Vital signs

Vital sign parameters include blood pressure, respiratory rate, pulse, temperature, and oxygen saturation level. Vital signs will be obtained as specified in the [Table 8-1](#). On Day 1, vital signs will be recorded pre-dose and monitored during and after the infusion.

Height and weight will be measured (supine or standing) at each study visit ([Table 8-1](#)). Screening weight shall be obtained at screening visit 2. On Day 1, weight and height will be measured pre-dose.

8.4.4 Other safety evaluations

Sural sensory nerve action potential (sural SNAP) is a conduction study commonly used to evaluate suspected peripheral neuropathies and will be performed in case sensory abnormalities, to complement neurologic examination ([Section 8.2.4](#)). Results will be read locally and must be captured in eCRF and as adverse event when criteria met per [Section 8.2.4](#). Central review to ensure consistent implementation and quality control of the neurophysiology data will be performed by an external expert. For details on SNAP assessments and quality checks, the sensory nerve conduction studies manual should be consulted.

8.4.5 Appropriateness of safety measurements

Safety assessments such as AEs, clinical laboratory assessments, ECGs, and vital signs are standard for this indication/participant population.

8.5 Additional assessments

8.5.1 Clinical Outcome Assessments (COAs)

As per [Section 4.7](#), during a Public Health emergency as declared by Local or Regional authorities i.e. pandemic, epidemic or natural disaster, that limits or prevents on-site study visits, COA data (e.g., neuromuscular module and multi-dimensional fatigue scale) may be collected remotely (e.g., web portal, telephone interviews) depending on local regulations, technical capabilities, and following any applicable training in the required process.

8.5.1.1 Hammersmith Functional Motor Scale-Expanded (HFMSE)

HFMSE was devised for use in children with SMA Type 2 and Type 3 to give objective information on motor ability and clinical progression ([Glanzman et al 2011](#)).

The HFMSE (2019 edition) assessment will be administered by the qualified site clinical evaluator (e.g., licensed physical or occupational therapist, or national equivalent) in accordance with the Schedule of Assessments ([Table 8-1](#)) for all participants ≥ 24 months of age. Participants < 24 months of age at time of visit will begin having HFMSE assessments as such time that 24 months of age is reached. The HFMSE is a short SMA-specific 33-item questionnaire that is easily administered by trained clinical evaluators. It requires minimal equipment, and is designed to factor in patient fatigue. Each motor skill item is scored on a 3-point Likert scale from 0 (no response) to 2 (full response), with a total score range of 0 to 66. A higher score indicates a higher level of ability.

8.5.1.2 Revised Upper Limb Module (RULM)

RULM is a validated, SMA specific assessment that measures motor performance in the upper limbs from childhood through adulthood in ambulatory and non-ambulatory individuals with SMA, and weaker individuals who have a floor effect or very low score on the Hammersmith Functional Motor Scale (HFMS) (Mazzone et al 2017). The RULM has a total of 19 scorable items: 18 items scored on a 0 (unable) to 2 (full achievement) scale, and one item that is scored from 0 (unable) to 1 (able). These item scores are summed to give a total score ranging from 0 to 37 points with lower scores reflecting poorer ability. The test is performed unilaterally using the limb preferred by the participant. The RULM will be administered by a site trained clinical evaluator (eg, licensed physical or occupational therapist, or national equivalent) in accordance with the Schedule of Assessments for all participants ≥ 24 months of age. Participants < 24 months of age at time of visit will begin having RULM assessments as such time that 24 months of age is reached.

For participants between 24-30 months of age the following two test items will not be administered and a Can Not Test (CNT) will be entered due to developmental limitations: (C)- tracing a path and (H)- tearing a paper. These items will be added into the assessment at ≥ 30 months of age.

8.5.1.3 Developmental milestone checklist

[figure not shown]
Developmental motor milestones will be assessed using relevant definition obtained from the World Health Organization Multicentre Growth Reference Study (WHO-MGRS) and Bayley Scales of Infant and Toddler Development - Third Ed (Bayley-III).

The Developmental Milestone Checklist will be completed by the qualified and trained site clinical evaluator (e.g., licensed physical or occupational therapist, or national equivalent) for all participants according to the Schedule of Assessments (Table 8-1).

Table 8-2 Developmental Milestone Checklist and Performance Criteria

Current Status Achieved	Developmental Motor Milestones: Bayley Scales of Infant and Toddler Development® Third edition (Bayley 2006) / WHO MGRS (2006)
YES/NO	Holds head erect for at least 3 seconds without support (Bayley GM #4)
YES/NO	Sits with slight support: 30 seconds (Bayley GM #19))
YES/NO	Sitting without support (WHO MGRS)
YES/NO	Sits without support: 30 seconds (Bayley GM #26)
YES/NO	Hands-and-knees crawling (WHO MGRS)
YES/NO	Pulls to stand (Bayley GM #35)
YES/NO	Standing with assistance (WHO MGRS)
YES/NO	Walking with assistance (WHO MGRS)
YES/NO	Standing alone (WHO MGRS)
YES/NO	Walking alone (WHO MGRS)
Developmental Milestone	Performance Criteria
Head control (Bayley, Gross Motor Item #4)	Child holds head erect for at least 3 seconds without support.
Sits with support (Bayley, Gross Motor Item #19)	Child sits with slight support for at least 30 seconds. Child may lose balance once or twice but is able to self-right (with your slight support).
Sitting without support (WHO MGRS)	Child sits up straight with the head erect for at least 10 seconds. Child does not use arms or hands to balance body or support position.

Sits without support: 30 seconds (Bayley, Gross Motor Item #26)	Child sits alone without support for at least 30 seconds. Child may lose balance once or twice but is able to self-right (does not fall over).
Hands-and-knees crawling (WHO MGRS)	Child alternately moves forward or backward on hands and knees. The stomach does not touch the supporting surface. There are continuous and consecutive movements, at least 3 in a row.
Pulls to Stand (Bayley, Gross Motor Item #35)	Child raises self to standing position using chair or other convenient object for support.
Standing with assistance (WHO MGRS)	Child stands in upright position on both feet, holding onto a stable object (e.g., furniture) with both hands without leaning on it. The body does not touch the stable object, and the legs support most of the body weight. Child thus stands with assistance for at least 10 seconds.
Walking with assistance (WHO MGRS)	Child is in upright position with the back straight. Child makes sideways or forward steps by holding onto a stable object (e.g., furniture) with 1 or both hands. One leg moves forward while the other supports part of the body weight. Child takes at least 5 steps in this manner.
Standing alone (WHO MGRS)	Child stands in upright position on both feet (not on the toes) with the back straight. The legs support 100% of the child's weight. There is no contact with a person or object. Child stands alone for at least 10 seconds.
Walking alone (WHO MGRS)	Child takes at least 5 steps independently in upright position with the back straight. One leg moves forward while the other supports most of the body weight. There is no contact with a person or object.

8.5.5 Pharmacokinetics

Not applicable.

DNA samples for genetic confirmation of SMA (mandatory)

The study includes a mandatory genetic research component.

Although participants are selected based on diagnostic testing results, it is possible that the diagnostic testing results needs to be confirmed during study process. The DNA sample collected may be used for genetic confirmation of SMA diagnosis and also be used for exon 7 modifier testing (current planned SMA genetic testing may not be able to detect *SMN1* point mutation).

The focus of the analysis is open and not pre-defined.

Laboratory manuals will be provided with detailed information on sample collection, handling, and shipment.

9 Study discontinuation and completion

9.1 Discontinuation and completion

9.1.1 Study treatment discontinuation and study discontinuation

Since this is a single dose study, discontinuation of study treatment is not applicable.

Because the study treatment is a single administration gene therapy, stopping or reversing the study treatment is not possible. Participants who decide they do not wish to participate in the study further should NOT be considered withdrawn from the study UNLESS they withdraw their consent (see 'Withdrawal of Informed Consent' section). Where possible, they should return for the Week 52/EOS assessments indicated in the Assessment Schedule (Table 8-1). If they fail to return for these assessments for unknown reasons, every effort (e.g., telephone, e-mail, letter) should be made to contact the participant/pre-designated contact as specified in the lost to follow-up section. This contact should preferably be done according to the study visit schedule.

If the participant cannot or is unwilling to attend any visit(s), the site staff should maintain regular telephone contact with the participant, or with a person pre-designated by the participant. This telephone contact should preferably be done according to the study visit schedule.

In the event of study discontinuation, the EOS study should be completed. At a minimum, in abbreviated visits, the following data should be collected at clinic visits or via telephone/email contact:

- New / concomitant treatments/medications
- AEs, including SAEs

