The study includes the option for the participant to have certain study procedures performed offsite by an off-site healthcare professional instead of at the study site, for which a separate signature is required if the participant agrees. It is required as part of this protocol that the Investigator presents this option to the participant, as permitted by national and local governing regulations. The process for obtaining consent should be exactly the same as described above for the main informed consent.

As per [Section 4.7](#), during a Public Health emergency as declared by Local or Regional authorities i.e. pandemic, epidemic or natural disaster, that may challenge the ability to obtain a standard written informed consent due to limits that prevent an on-site visit, Investigator may conduct the informed consent discussion remotely (e.g. telephone, videoconference) if allowable by a local Health Authority.

Guidance issued by local regulatory bodies on this aspect prevail and must be implemented and appropriately documented (e.g. the presence of an impartial witness, sign/dating separate ICFs by trial participant and person obtaining informed consent, etc.).

8 Visit schedule and assessments

The Assessment Schedule ([Table 8-1](#)) lists type and timing of all assessments. All data obtained from these assessments must be supported in the participant's source documentation.

Participants should be seen for all visits/assessments as outlined in the assessment schedule ([Table 8-1](#)) or within the specified visit window. Missed or rescheduled visits should not lead to automatic discontinuation. Participants who prematurely discontinue the study for any reason should be scheduled for a visit as soon as possible, at which time all of the assessments listed for the final visit will be performed. At this final visit, the AE and concomitant medications recorded on the CRF.

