2.1.1 General definitions

Investigational drug is the study drug OAV101 at 1.1e14 vg/kg.

Study day is the number of days from the Day 1 +1, if after Day 1, where Day 1 is the day of single administration of investigational drug. Study day is the negative number of days to Day 1, if before Day 1.

“Baseline” refers to a non-missing measurement or evaluation made prior to initiation of OAV101 infusion. If there are multiple measurements prior to the initiation of OAV101

infusion, only the latest measurement will be considered as baseline for analysis purposes. If these multiple measurements occur at the same time or time is not available, then the average of these measurements (for continuous data) or the worst among these measurements (for categorical data) will be considered as the baseline value. This same baseline value will be used throughout the study periods.

Change from baseline is defined as post-baseline value minus baseline value.

“Last contact” refers to the last study visit. If not terminated early, it is the end-of-study visit.

Analysis visits are defined following a visit windowing approach based on study day post dosing. For by-visit endpoints, the time windows describe how data will be assigned to protocol-specified time points during follow up.

Per week, the time windows for endpoints assessed at all visits are around the nominal Study Days as follows:

Visit	Nominal day	Start day	End day
Week 1	Day 8	Day 4	Day 11
Week 2	Day 15	Day 12	Day 18
Week 3	Day 22	Day 19	Day 25
Week 4	Day 29	Day 26	Day 36
Week 6	Day 43	Day 37	Day 50
Week 8	Day 57	Day 51	Day 64
Week 10	Day 71	Day 65	Day 82
Week 13	Day 92	Day 83	Day 137
Week 26	Day 183	Day 138	Day 228
Week 39	Day 274	Day 229	Day 319
Week 52	Day 365	Day 320	Day 455

For efficacy endpoints to be assessed at Weeks 4, 13, 26, 39, and 52 only, visit windows are defined as

Visit	Nominal day	Start day	End day
Week 4	Day 29	Day 4	Day 60
Week 13	Day 92	Day 61	Day 137
Week 26	Day 183	Day 138	Day 228
Week 39	Day 274	Day 229	Day 319

Week 52	Day 365	Day 320	Day 455
---------	---------	---------	---------

For ECG and echocardiogram endpoints to be assessed at Weeks 1, 4, 8, 13, 26, and 52 only, visit windows are defined as

Visit	Nominal day	Start day	End day
Week 1	Day 8	Day 4	Day 18
Week 4	Day 29	Day 19	Day 42
Week 8	Day 57	Day 43	Day 74
Week 13	Day 92	Day 75	Day 137
Week 26	Day 183	Day 138	Day 273
Week 52	Day 365	Day 274	Day 455

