If more than one observation for a specific assessment is included in a time window, the assessment closer to the nominal time will be used. If there are two observations equally distant to the nominal time, the latest one will be used in analyses.

An “Adverse Event” (AE) is any untoward medical occurrence in a clinical investigation subject, which does not necessarily have a causal relationship with the drug or device under study.

A “treatment-emergent Adverse Event” is any AE whose onset or worsening occurred on or post Day 1.

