2.5.3 Handling of intercurrent events

For AEs, SAEs, important identified and important potential risks, intercurrent events will not be considered following a treatment policy strategy.

Use of prohibited concomitant medications with an impact on safety: Data collected while/after receiving prohibited concomitant medications with an impact on safety will be included in the analyses of AEs (treatment policy strategy).

Study discontinuation due to reasons other than death: Data collected up to the point of discontinuation will be included in all primary endpoint analyses.

Study discontinuation due to death: It is anticipated that this intercurrent event is unlikely to occur during the study. Data collected up to the point of death will be included in all primary endpoint analyses.

Changes from baseline in vital signs, clinical laboratory, and procedure results will be summarized for all data available, only excluding data collected after the start of intake of prohibited medication, if any, following a hypothetical strategy and assuming this intercurrent event occurring at random.

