2.7.3 Laboratory data

Safety laboratory data generated by the central laboratory will be used in all analyses. Safety laboratory data generated by local lab will only be listed. In data listings, per parameter, values will also be given as multiples of upper normal range limits.

Laboratory parameters include hematology, chemistry and urinalysis variables.

Changes in selected safety laboratory variables are primary endpoints. For details, see Section 2.5.

Hematology variables include: hematocrit, hemoglobin, red blood cell (RBC) count, white blood cell (WBC) count, differential blood count (in measured values and % of WBC; neutrophils, lymphocytes, monocytes, eosinophils, basophils, bands), mean corpuscular volume

(MCV), mean corpuscular hemoglobin (MCH), mean cell hemoglobin concentration (MCHC), and platelets.

Chemistry variables include: ALT, ALP, AST, blood urea nitrogen (BUN), calcium, creatinine, gamma glutamyl transferase, glucose, serum total bilirubin, direct bilirubin, indirect bilirubin, total creatine kinase (CK), chloride, phosphorus, sodium, potassium, lactate dehydrogenase (LDH), GLDH, troponin-I, and bicarbonate.

Urinalysis variables include: specific gravity, pH, ketones, glucose, protein, blood, leukocyte esterase, nitrites, bilirubin, RBC count, WBC count, yeast, squamous epithelial cells, casts, crystals, bacteria.

Clinical laboratory test results will be summarized at each visit including End of Study/Early Termination, for minimum, maximum and final post-baseline values. Urinalysis variables will only be listed.

Laboratory data values will be categorized as low, normal, or high, based on normal ranges of the laboratory used in this study. Shift tables from baseline to minimum value, maximum value, and final values will be created. The shift tables will cross tabulate the frequency of participants with baseline values below/within/above the normal range versus minimum/maximum/final values below/within/above the normal range.

The number and percentage of participants meeting the criteria for ALT and bilirubin defined in Table 16-1 of the protocol will be summarized by weight bracket and overall including potential Hy's Law cases. Potential Hy's Law cases will be presented for maximum post-baseline values as combined, even if criteria are fulfilled at different times during the follow-up.

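### Results from an early final visit can drop out of the by-visit tables for every endpoint except laboratory data; a final-value row would keep them in (minor)

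*Protocol*

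**What the plan says.** **Protocol.** Section 9.1.1: "In the event of study discontinuation, the EOS study should be completed". It also allows abbreviated contacts that collect only medications and adverse events, and asks children who stop taking part to come back for Week 52/EOS where possible. Section 8 sets a different timing: such children "should be scheduled for a visit as soon as possible, at which time all of the assessments listed for the final visit will be performed". Table 8-1 lists ECG, echocardiogram, HFMSE, RULM and the milestone checklist at Week 52/EOS. It has no Week 39 ECG or echocardiogram.

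**SAP 2.1.1.** "Analysis visits are defined following a visit windowing approach based on study day post dosing". The windows adjoin without gaps. "If more than one observation for a specific assessment is included in a time window, the assessment closer to the nominal time will be used". The later record wins only on a tie: "If there are two observations equally distant to the nominal time, the latest one will be used in analyses". Nothing is said about an early-termination visit.

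**SAP 2.5.3**, on leaving for reasons other than death: "Data collected up to the point of discontinuation will be included in all primary endpoint analyses". The same section bases changes in vital signs, laboratory values and procedures on everything available apart from data after prohibited medication. SAP 2.6.3 says much the same for HFMSE, RULM and milestones.

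**SAP 2.7.3**, laboratory data only: "Clinical laboratory test results will be summarized at each visit including End of Study/Early Termination, for minimum, maximum and final post-baseline values". SAP 2.5.2, 2.6.2 and 2.7.4 provide no such summary for the other endpoints.

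**The concern.** The protocol asks families for a full last assessment, and the SAP may then leave it out of every by-visit summary except the laboratory ones. The scheduled visit in a window normally comes first and lies nearer the nominal day. An early final visit later in that window therefore loses.

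The gap is widest for the heart. Because there is no Week 39 ECG or echocardiogram, a recording made when a child leaves between Days 184 and 273 is the only protocol-required cardiac recording after Week 26. The Week 26 cardiac window runs to Day 273, so an on-time Week 26 recording displaces it. Cardiac adverse events are one of the named risks.

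For HFMSE and RULM, the mixed model would treat the earlier score as that child's last observation. Brackets hold 6 to 10 children and leavers are not replaced, so one record carries weight. The SAP has already solved the problem for laboratory data, and a programmer following 2.1.1 strictly would have trouble honouring 2.5.3 for the rest.

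**Working it through.** **1. Figures in the plan.** The documents give no figure for lost final assessments and no dropout rate. The one design figure is a 90% chance of seeing at least one event of 9% incidence in about 24 children. It reproduces: 1 − 0.91^24 = 0.896 (0.941 for 30). The point does not depend on it; only the 24-30 children are used below.

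**2. When a final assessment is lost.** Let the final visit fall on day t, in a window with nominal day m, and let the scheduled visit in that window have taken place on day v < t. The final assessment is not selected if |v − m| < |t − m|. If v = m, that holds on every day from m + 1 to the window's end. If t falls before the next nominal day but already inside that visit's window, the final assessment is kept under that visit's label.

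**3. Days lost with scheduled visits on their nominal days** (windows from SAP 2.1.1; leaving on Days 4-364, which is 361 days):

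| Endpoint | Days lost in successive windows | Total | Share |
|---|---|---|---|
| Vital signs | 3+3+3+7+7+7+11+45+45+45 | 176 | 176/361 = 48.8% |
| HFMSE, RULM, milestones | 31+45+45+45 | 166 | 166/361 = 46.0% |
| ECG, echocardiogram | 10+13+17+45+90 | 175 | 175/361 = 48.5% |

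For motor endpoints the lost days are 30-60, 93-137, 184-228 and 275-319. For ECG and echocardiogram the last and longest run is Days 184-273. Counting only leaving on Days 30-364 gives 49.9%, 49.6% and 49.3%.

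**4. Looser timing and attendance.** The same count was repeated with scheduled visits spread evenly over the Table 8-1 tolerances (±2, ±5 or ±14 days) and leaving on Days 4-364:

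| Endpoint | Preceding visit always attended | Attended by 80% |
|---|---|---|
| Vital signs | 37.6% | 0.8 × 37.6 = 30.1% |
| HFMSE, RULM, milestones | 39.6% | 0.8 × 39.6 = 31.7% |
| ECG, echocardiogram | 43.0% | 0.8 × 43.0 = 34.4% |

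The share is 0% if the final visit coincides with a scheduled visit or the child returns at Week 52.

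**5. Number of children.** Assume 5-20% of 24-30 children leave: 0.05 × 24 = 1.2 up to 0.20 × 30 = 6. With a 39-49% share, 1.2 × 0.39 = 0.47 and 6 × 0.49 = 2.94, so about 0.5 to 3. At 80% attendance the low end is 1.2 × 0.30 = 0.36.

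**6. Scale of one record.** As an illustration only, a 6-point HFMSE difference in either direction between the selected and the unselected result equals 6/10 = 0.6 to 6/6 = 1.0 points of a bracket mean. Six points is one of the change thresholds tabulated in SAP 2.6.2, not an expected effect.

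**The case against.** Nearest-to-nominal selection is a standard, defensible rule, and it applies to every repeat assessment, not only to leavers. SAP 2.5.3 deals with intercurrent events. It can be read as saying only that leaving does not remove data already collected, not that every record enters every visit mean. On that reading there is tension between the sections but no flat contradiction. This stands, and it is why the rule itself should stay.

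A reader might infer more than the documents support:

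- *That half of all early final assessments are lost.* This is the top of the range. It needs on-time attendance, evenly spread leaving dates and a separate visit with full assessments. Protocol 9.1.1 allows abbreviated contacts and a return at Week 52.
- *That motor or safety results are made to look better.* Nothing shows that leavers decline. Protocol 4.6 reports continuing milestone gains after treatment, so the omitted result could equally be the better one.
- *That a safety problem at the final visit would vanish.* All individual data are listed (SAP 2.1), and clinically significant findings are to be reported as adverse events, which are not windowed. SAP 2.6.2 plans individual HFMSE and RULM trajectories. The SAP does not say that these, the QTcF > 500 ms summaries or the vital-sign flags are limited to selected records.

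The child also still contributes the earlier result in that window. None of this explains why laboratory data alone get a final-value summary.

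**Conclusion.** The point holds as a minor one. Under SAP 2.1.1, an early final visit that follows an on-time scheduled visit in the same window is left out of the by-visit summaries of vital signs, ECG, echocardiogram, HFMSE, RULM and milestones. Only laboratory data are protected. That fits poorly with the inclusion statements in SAP 2.5.3 and 2.6.3.

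The size rests on assumptions: evenly spread leaving dates, a full final visit for each leaver, and a leaving rate that the documents do not give. Under these, roughly 30-50% of early final assessments are affected, or about 0.5 to 3 children. The direction is unknown. No hypothesis is tested, so no formal conclusion turns on it. The loss is of one result per endpoint for a leaver, not of the child, and it can be recovered from the listings.

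**What to change.** 1. **SAP 2.1.1:** keep the nearest-to-nominal rule and state that it governs the by-visit tables only.
2. **SAP 2.5.2, 2.6.2 and 2.7.4:** extend the End of Study/Early Termination and final post-baseline summary of 2.7.3 to vital signs, ECG, echocardiogram, HFMSE, RULM and milestones.
3. **SAP 2.5.3 and 2.6.3:** refer to that summary as the place where results from an early final visit are included, so that these sections agree with 2.1.1.
4. **Protocol Sections 8 and 9.1.1:** reconcile the timing of the final visit for a child who leaves early.

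Do not substitute the early final result for an on-time scheduled one. That would discard a valid record and make selection depend on dropout. It could also label a Day 273 echocardiogram as Week 26 for leavers only.

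The cost is SAP wording, one extra row per table and a protocol clarification, with no new data. The drawback is that final values come from differing follow-up times, so the row should be labelled accordingly.
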